Observational Study Protocol CV185266

RISK OF STROKE AND OTHER CARDIOVASCULAR EVENTS AMONG WARFARIN-TREATED ATRIAL FIBRILLATION PATIENTS- A NATIONWIDE COHORT STUDY IN FINLAND

Study Director

[name] PhD
Helsinki University Central Hospital
Telephone (office): [name] (central)
[contact]
[contact]

Protocol Manager

[name]
Telephone (office): [name]
[contact]
[contact]

External Investigator/CRO

[name], Adj. Prof.
EPID Research
[name]
Telephone (office): [contact]
[contact]

Bristol-Myers Squibb Research and Development

[name]
[name]

This document is the confidential and proprietary information of Bristol-Myers Squibb Company and its global affiliates (BMS). By reviewing this document, you agree to keep it confidential and to use and disclose it solely for the purpose of assessing whether your organization will participate in and/or the performance of the proposed BMS-sponsored study. Any permitted disclosures will be made only on a confidential "need to know" basis within your organization or to your independent ethics committee(s). Any other use, copying, disclosure or dissemination of this information is strictly prohibited unless expressly authorized in writing by BMS. Any supplemental information (e.g., amendments) that may be added to this document is also confidential and proprietary to BMS and must be kept in confidence in the same manner as the contents of this document. Any person

who receives this document without due authorization from BMS is requested to return it to BMS or promptly destroy it. All other rights reserved.

SYNOPSIS

Observational Study Protocol CV185266

Protocol Title: Risk of stroke and other cardiovascular events among warfarin-treated atrial fibrillation patients – a nationwide cohort study in Finland

Department: BMS Medical, Finland

Objective(s):

Primary objectives:

- 1) To investigate and compare risk of stroke, systemic thromboembolism, and myocardial infarction among atrial fibrillation (AF) patients in relation to International Normalized Ratio (INR) levels: under 2.0, 2.0-3.0, and over 3.0.
- 2) To investigate and compare risk of bleeding events among AF patients in relation to INR levels: under 2.0, 2.0-3.0, and over 3.0.
- 3) To investigate and compare mortality risk among AF patients in relation to INR levels: under 2.0, 2.0-3.0, and over 3.0.

Secondary objectives

- 1) To investigate risk of stroke, systemic thromboembolism, myocardial infarction, and bleeding events among AF patients during the first 90 days after initiation of warfarin treatment.
- 2) To investigate risk of stroke, systemic thromboembolism, myocardial infarction, and bleeding events among AF patients in relation to time from AF diagnosis to time of initiation of warfarin treatment.
- 3) To investigate risk of stroke, systemic thromboembolism, myocardial infarction, and bleeding events among AF patients who have stopped using warfarin.

Study Design: The study is conducted as a nationwide retrospective register-based linkage study using data obtained from the Finnish health care registers. The study population consists of all AF patients using warfarin with INR measurements in selected hospital district areas in Finland between 01-Jan-2007 and 31-Dec-2009 with up to 5 years follow-up.

Study Population:

Inclusion criteria: Patients who:

- have purchased warfarin (ATC code B01AA03) between 01-Jan-2007 and 31-Dec-2009,
- have at least one INR measurement between 01-Jan-2007 and 31-Dec-2009, and
- have ICD-10 diagnosis I48 for AF between 01-Jan-2005 and 31-Dec-2009.

Exclusion criteria: Permanent residence in Finland less than 12 months prior to index date. Age below 18 years at index date.

Data Collection Methods:

This is a fully register-based study and patients will not be contacted in any phase of the study.

- Patients with warfarin exposure will be identified by Kela, who then will convert the patient IDs to study IDs (SIDs). Kela will then send the IDs and the SIDs to other register holders: Statistics Finland, National Institute for Health and Welfare, Statistics Finland, Population Register Center, Finnish Cancer Registry, and central hospital laboratories included in the study.

- EPID Research will receive unidentifiable data including SIDs only.
- All patient data are then anonymous which ensures full data protection of the patients.
- Approval of Ethical Review Board of Hospital District of Helsinki and Uusimaa (HUS) will be requested to cover the nationwide study.
- Data permits will be requested from each registry holder based on the study protocol and ethical approval.
- Index date is defined as the date of first purchase of warfarin after 01-Jan-2007. Follow-up of the patients starts on the index date, and ends on 31-Dec-2011, at time of death or at time of emigration whichever occurs first. Treatment and comorbidity history is gathered from the period 01-Jan-2005 and 31-Dec-2006.

Data Analyses: Stratified incidence rates with 95% CIs will be estimated for each endpoint within the strata of the INR levels, time in therapeutic INR range (TTR) categories, and other covariates.

The crude and adjusted hazard ratio (HR) estimates with 95% CIs and P-values will be estimated within the INR levels and TTR categories using the conventional Cox's proportional hazards model adjusting for other covariates. For INR the category 2.0–3.0 will be used as the reference category. Similarly for TTR the category $\geq 60\%$ of time will be used as the reference category.

Sample Size/Power: According to the power calculations we are able to detect 10-20% differences in the main endpoints with sufficient power of approximately 80% or higher.

Limitations/Strengths:

- No exact prescribed dosages are available. Warfarin exposure is assumed based on the information of purchases and package sizes with defined daily doses (DDDs).
- Fully reliable information on eg, acetylsalicylic acid use is not available because the data of the prescription register exclude relatively inexpensive packages and over the counter medications which are not reimbursed.
- Medications used during hospitalizations are not available. However, based on the hospital care register the hospitalization periods can be taken into account to define gaps in the drug treatment periods.
- The laboratory data are collected from separate local central laboratories. Changes in places of domicile may affect the follow-up of the patients. On the other hand, previous published surveys on the subject have not included INR follow-up to this extent.

TABLE OF CONTENTS

TITLE PAGE	1
SYNOPSIS.....	3
TABLE OF CONTENTS.....	5
1 INTRODUCTION	7
1.1 Study Rationale.....	7
1.2 Research Question	7
2 OBJECTIVES.....	8
2.1 Primary Objectives.....	8
2.2 Secondary Objectives.....	8
2.3 Exploratory Objectives	8
3 STUDY DESIGN.....	8
3.1 Overview of Study Design.....	8
3.2 Study Population.....	9
3.2.1 Inclusion Criteria.....	9
3.2.2 Exclusion Criteria.....	9
3.3 Data Source/Data Collection Process	9
3.4 Definitions of Study Variables.....	11
3.4.1 Outcomes/Endpoint Variables	11

1 INTRODUCTION

1.1 Study Rationale

Atrial fibrillation (AF) resulting in an increased risk of stroke and systemic thromboembolism is the most common indication for warfarin treatment. Anticoagulant treatment, while decreasing the risk of embolic events, increases the risk of bleeding complications.

The benefits of a Vitamin K antagonist (VKA), such as warfarin, depend on maintaining the International Normalized Ratio (INR) within a relatively narrow range. It has been shown that the optimal INR target range is between 2.0 and 3.0 for AF patients.¹ This range has been implemented into common clinical practice in Finland from 2000 onwards. Considering INR data at the time of the event, an INR below 2.0 decreases the benefit of VKA for prevention of strokes, whereas an INR above 3.0 increases the risk for serious bleeding complications. Due to the pharmacokinetic variability of warfarin and its interactions with many drugs and foods, as well as inter individual differences among patients, it may be difficult to maintain the INR in this therapeutic range.^{2,3} It has been described that only about 63% of AF patients receive appropriate anticoagulation treatment,⁴ and that even with adequate INR monitoring the time in therapeutic range (TTR) is generally less than 60%.⁵ The Social Insurance Institution of Finland considers warfarin treatment balance to be satisfactory if TTR of 60% is reached in steady state.⁶ The treatment with other anticoagulants other than warfarin, ie, treatment with new oral anticoagulant treatments (NOACs), is reimbursed only as a second-line treatment if this balance is not achieved. The TTR is generally high in Nordic countries.⁷ In Finland, any data of performance of anticoagulation therapy assessed with TTR has not been published, but it has previously been shown in Helsinki area that 63% of all outpatient INR measurements were at the target between 2.0-3.0 and 70% between 1.9–3.5.⁸

The present study is the first nationwide register-based cohort study in Finland focusing on AF. The study provides real world data on current anticoagulation treatment practices, treatment balance, and its consequences in whole Finland. Evidence on TTR through INR monitoring specifically addresses the reimbursement question and the possible unmet medical need for new oral anticoagulation treatment of AF patients.

1.2 Research Question

The aim of this study is to evaluate the incidence and risk of stroke, systemic thromboembolic events, myocardial infarction, bleeding events, and mortality in relation to management of warfarin therapy among AF patients. INR target is defined as 2.0-3.0 according to current care treatment guidelines.^{9,10} The risks mentioned above are separately evaluated with different management levels of warfarin therapy. The study population is also characterized according to comorbidity, interactive medications and antiarrhythmic drugs in use. Additional study questions are related to initiation, discontinuation, and duration of warfarin treatment. The incidence of anemia and renal impairment in association with warfarin use will also be studied.

2 OBJECTIVES

2.1 Primary Objectives

- 1) To investigate and compare risk of stroke, systemic thromboembolic events, and myocardial infarction among AF patients in relation to INR levels: under 2.0, 2.0-3.0, and over 3.0.
- 2) To investigate and compare risk of bleeding events among AF patients in relation to INR levels: under 2.0, 2.0-3.0, and over 3.0.
- 3) To investigate and compare mortality risk among AF patients in relation to INR levels: under 2.0, 2.0-3.0, and over 3.0.

The primary objectives are evaluated separately for prevalent users of warfarin and for new users of warfarin.

2.2 Secondary Objectives

- 1) To investigate risk of stroke, systemic thromboembolic events, myocardial infarction, and bleeding events among AF patients during the first 90 days after initiation of warfarin treatment.
- 2) To investigate risk of stroke, systemic thromboembolic events, myocardial infarction, and bleeding events among AF patients in relation to time from AF diagnosis to time of initiation of warfarin treatment.
- 3) To investigate risk of stroke, systemic thromboembolic events, myocardial infarction, and bleeding events among AF patients who have stopped using warfarin.

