3 STUDY DESIGN

3.1 Overview of Study Design

The study with cohort design is conducted as a nationwide retrospective register-based linkage study using data obtained from the Finnish health care registers. The study population consists of all AF patients using warfarin with INR measurements in selected hospital district areas in Finland between 01-Jan-2007 and 3-Dec-2009.

Index date: Index date is defined as the date of first purchase of warfarin after 01-Jan-2007.

Follow-up period: Follow-up of the patients starts on the index date, and ends on 31-Dec-2011, at time of death or at time of emigration whichever occurs first.

History period: Treatment and comorbidity history is gathered from the period 01-Jan-2005 through 31-Dec-2006.

The key milestones of the study process are given below (Table 3.1-1). Note that the timelines are estimates only and are subject to change depending on the duration of the data permission processes and actual receipt of the data from the register holders.

Table 3.1-1: Study Timelines

Milestone	Anticipated date
Study protocol approved	4-Mar-2013
Registration in the ENCePP e-Register	30-Apr-2013
Ethics committee approval	30-Apr-2013
Data permit approvals	30-Jun-2013
Receipt of data from register holders	30-Sep-2013
Final study report	30-Dec-2013

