3.4.3 Other Covariates/Control Variables

- Reimbursement code 207
 - Yes/no
- Information about hospitalizations and institutionalization (other than hospitalization)

- dates
- will be taken into account when defining the discontinuation of warfarin treatment
- Laboratory parameters for anemia characterizations
 - Blood picture
 - ◆ Haemoglobin
 - decrement of 20 g/L
 - being under the reference value
 - See [Appendix 2](#) for details.
- Concomitant use of class D interactive drugs according to SFINX (Swedish, Finnish, INteraction X-referencing, see [Appendix 3, Table 3](#) for complete ATC listing)
 - Concomitant use during the warfarin treatment period assumed by the purchases and exposure (see definition for exposure in Section 4.1).
- Age*
- Gender*
- Hospital district
 - Helsinki, Turku, Tampere, Kuopio, Oulu, Jyväskylä
 - other possible central hospitals
- CHADS₂^{11 12}
- CHA₂DS₂-VASc^{11,12}
- Comorbidities (more in detail in [Appendix 4](#))
 - Hypertension*
 - Thyrotoxicosis
 - Cardiomyopathy
 - Congestive heart failure*
 - Diabetes*
 - Stroke*
 - Transient ischemic attack*
 - Vascular disease**
 - Cancer
 - Venous thromboembolism
 - *included in CHADS₂ score and in CHA₂DS₂-VASc score
 - **included in CHA₂DS₂-VASc score.

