4 STATISTICAL ANALYSIS

4.1 Statistical Analysis Methods

Data management, tabulations, graphics, and statistical modeling in carried out with R language (<http://www.r-project.org>). R language is described more detailed in report "R: Regulatory

Compliance and Validation Issues: A Guidance Document for the Use of R in Regulated Clinical Trial Environments" (<http://www.r-project.org/doc/R-FDA.pdf>)

A separate statistical analysis plan (SAP) including detailed statistical analysis and outputs will be produced by EPID research prior to performing any analysis.

Study population: The study population will be described at baseline (start of follow-up) using by previous drug exposure and other covariates.

Study outcomes: All study outcomes will be summarized by drug exposure and other covariates.

Drug exposure: Drug exposure starts at date of purchase. The length of the exposure period is calculated as $DDD/dose \times 1.5$, where DDD (daily defined dose) is the total amount purchased and “dose” is the amount used daily (one for an average person). For the first purchase “dose=1” and for other purchases the “dose” is calculated from previous use by dividing the previous DDD with the time between the present and the previous purchase.

The impact of the multiplier 1.5 in the construction of drug exposure will be evaluated for the primary objectives in sensitivity analyses by using multiplier values 1.25, 1.5 and 2. We will also perform a sensitivity analysis for the primary objectives by including only those patients with at least two purchases of prescriptions within a clinically meaningful timeframe of 3 months after the index date.

INR levels: Daily INR levels are calculated:

- 1) As the previous recorded INR measurement
- 2) By linear interpolation between two consecutive INR measurements. If the gap between the measurements is more than 60 days the previous measurement is applied.

Daily INR estimates are categorized into levels: under 2.0, 2.0-3.0, over 3.0. In addition when appropriate a finer categorization is used: under 1.5, 1.5-2.0, 2.0-3.0, 3.0-4.0, 4.0-5.0, 5.0-9.0, and over 9.0. This finer categorization will be used only in the analysis of the primary objectives.

Time in therapeutic range (TTR): The INR target value for AF patients is 2.0-3.0. In addition for stroke, systemic thromboembolic events, and myocardial infarction INR target above 2.0 is considered and for bleeding events INR target under 3.0 is considered.

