4.1.1 Primary Objective

Objectives 1-3: Stratified incidence rates with 95% confidence intervals (CIs) will be estimated for each primary endpoint within the strata of the exposure variables (INR levels and TTR categories) and other covariates, including history of AF prior the index date.

The crude and adjusted hazard ratio (HR) estimates with 95% CIs and P-values will be estimated separately within the INR levels and TTR categories using the conventional Cox's proportional hazards model adjusting for other covariates. For INR the category 2.0–3.0 will be used as the reference category. Similarly for TTR the category $\geq 60\%$ of time will be used as the reference category.

The objectives will be evaluated separately for the prevalent warfarin user population and the new warfarin user population. The new warfarin user population consists of those patients who initiate warfarin treatment during the follow-up (01-Jan-2007 to 31-Dec-2009).

A further sensitivity analysis will be performed where the adjusted HRs are estimated stratifying by the history of AF prior to the index date.

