4.1.3 Exploratory Objectives

Objective 1: Stratified incidence rates with 95% CIs will be estimated for anemia as endpoint within the strata of the exposure variables (INR levels and TTR categories) and other covariates.

The crude and adjusted hazard ratio (HR) estimates with 95% CIs and P-values will be estimated separately within the INR levels and TTR categories using the conventional Cox's proportional hazards model adjusting for other covariates. For INR the category 2.0–3.0 will be used as the reference category. Similarly for TTR the category $\geq 60\%$ of time will be used as the reference category.

Objective 2: Discontinuity period of warfarin treatment due to a surgical operation or intervention is identified as starting two weeks before and ending two weeks after such procedure.

Stratified incidence rates with 95% CIs will be estimated for stroke, systemic thromboembolic events, myocardial infarction, and bleeding events in the strata of other covariates within periods of warfarin discontinuity. Also, an indicator variable of the discontinuity period will be added to the Cox's proportional hazards model.

Sensitivity analysis will be done to study the robustness of the discontinuity period definition.

Objective 3: The distribution of days taken to achieve INR target in the new warfarin user population will be provided. Stable INR-target is considered achieved after 3 consecutive INR measurements are within the target 2.0-3.0.

Objective 4: For the new warfarin user population the distribution of TTR at 1, 6, and 12 months after start of warfarin treatment stratified by other covariates. For the prevalent warfarin user population the distribution of TTR at the end of 2010 and 2011 stratified by other covariates.

Objective 5: Warfarin users will be tabulated by use of antiarrhythmic medication (yes/no) at start of follow-up and during follow-up. During follow-up users will also be stratified by the INR and the TTR levels.

Objective 6: Warfarin users will be tabulated by use of interaction medication (yes/no) at start of follow-up and during follow-up. During follow-up users will also be stratified by the INR and the TTR levels.

Objective 7: Warfarin users will be tabulated by comorbidities.

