5 STUDY LIMITATIONS/STRENGTHS

Finland has a well-developed population register system with tens of years of longitudinal follow-up data. The persons are identified in the registers with a unique personal identification number enabling linkage between different registers. These data has not been collected for study purposes, which may affect the quality of the data. However, these registers have been considered reliable for scientific research purposes.

Only those citizens that have been living in Finland for 12 months prior to index date will be included in the study.

No exact prescribed dosing information is available. Dosing is assumed based on the information of purchases and package sizes with defined daily doses (DDDs).

Coverage of the Prescription Register containing reimbursement information of all permanent residents of Finland is about 97%. Missing data includes relatively inexpensive packages which are not reimbursed. Fully reliable information on eg, acetylsalicylic acid use is then not available.

Medications used during hospitalizations are not available. However, based on the hospital care register the hospitalization periods can be taken into account to define gaps in the drug treatment periods.

No nationwide database about laboratory measurements is available. The laboratory data is then collected from separate local central laboratories. All laboratory values for particular patients may then not be available. Also changes in places of domicile may affect the follow-up of the patients. On the other hand, previous published surveys on the subject have not included INR follow-up to this extend.

To avoid selection bias, the cohort time (years 2007 to 2009) was chosen to avoid complication of patients switching from warfarin to newer anticoagulant medications eg, dabigatran.

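### Warfarin start is in effect dated at first pharmacy purchase, so new users started in hospital enter the first-90-day and days-to-INR-target analyses late, with bias of uncertain size and direction

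*Protocol*

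**What the plan says.** Protocol Section 3.1 sets time zero: "Index date is defined as the date of first purchase of warfarin after 01-Jan-2007". Section 4.1 does the same for exposure: "Drug exposure starts at date of purchase". No separate initiation date is given for the new-user population (4.1.1), for the 90-day analysis (4.1.2 Objective 1) or for time to target (4.1.3 Objective 3).

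The Synopsis and Section 5 both concede: "Medications used during hospitalizations are not available". The remedy offered in Section 5 is that "based on the hospital care register the hospitalization periods can be taken into account to define gaps in the drug treatment periods". Section 3.4.3 says of hospitalization and institutionalization dates that they "will be taken into account when defining the discontinuation of warfarin treatment". Neither place applies those dates to the start of treatment.

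Two analyses depend on the start date. Secondary Objective 1 covers stroke, systemic thromboembolic events, myocardial infarction and bleeding "among AF patients during the first 90 days after initiation of warfarin treatment". For Exploratory Objective 3, "The distribution of days taken to achieve INR target in the new warfarin user population will be provided", with target reached after three consecutive INRs of 2.0-3.0.

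**The concern.** A patient who receives the first dose on a ward and buys warfarin after discharge has already passed through part of the initiation phase by the index date. A stroke or bleed in those days precedes follow-up and is not counted. A patient who dies before any purchase fails the inclusion criterion in Section 3.2.1 and never enters. This is left truncation over the very days Secondary Objective 1 is meant to describe.

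Exploratory Objective 3 has the same misplaced clock. Ward starters and outpatient starters are also pooled in one table on different time zeros, under a label that is accurate only for the second group. Some ward starts are a reasonable expectation, because AF diagnoses are taken from the care register (Section 3.3), but the protocol does not say how many.

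**Working it through.** The protocol states no figure for the share started in hospital, the lag to first purchase, the early hazard, the 90-day risk or the days to target. There is nothing to reproduce, and every input below is an assumption.

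**Inputs (assumed)**
- L, days from first dose to first purchase in hospital starters: 3, 7 or 10.
- k, daily event rate in those L days relative to later days: 1, 2 or 4.
- p, share of new users started in hospital: 20-60%.
- Events are rare enough to ignore depletion, and hospital and outpatient starters have the same underlying risk.

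**90-day events in hospital starters**

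The true window is days 0 to 90 from first dose. In units of the later daily rate it expects L·k + (90 − L). The observed window is days L to L + 90. It loses the first L days but gains L days at its end, so it expects 90. Net shortfall = 1 − 90/(L·k + 90 − L).

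| L | k | True | Observed | Share of true events before purchase | Net shortfall |
|---|---|---|---|---|---|
| 3 | 1 | 3 + 87 = 90 | 90 | 3/90 = 3.3% | 0% |
| 7 | 2 | 14 + 83 = 97 | 90 | 14/97 = 14.4% | 7.2% |
| 10 | 4 | 40 + 80 = 120 | 90 | 40/120 = 33.3% | 25% |

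The last column is the bias in the reported figure. The column before it is not.

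**All new users**

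Multiply by p. Central case (L = 7, k = 2): 0.2 × 7.2% = 1.4% to 0.6 × 7.2% = 4.3%. Most extreme row (L = 10, k = 4): 0.2 × 25% = 5% to 0.6 × 25% = 15%.

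**Sensitivity to the shape of the hazard**

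Let the rate be k times the later rate for days 0-30 whatever the purchase date, with p = 10-50% and L = 3-14. The ratio of observed to true 90-day risk over all new users is then:
- k = 3: 0.907 to 0.996. At the lower end (L = 14, p = 50%), true = 30 × 3 + 60 = 150 and observed = 16 × 3 + 74 = 122. The ratio is 0.813 in hospital starters and 1 − 0.5 × 0.187 = 0.907 overall.
- k = 2: 0.942 to 0.998.
- k = 1: 1.000.
- k = 0.5: 1.002 to 1.047, a slight overstatement.

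The sign therefore depends on whether the hazard falls after the first dose.

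**Days to target**

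If in-hospital INRs count and the target is reached after purchase, each hospital starter's time is short by L and the mean over all new users by p × L: 0.2 × 3 = 0.6 to 0.6 × 10 = 6.0 days. If only INRs after purchase count, three further in-range values are needed even from a patient already in range. The end point then moves later, and the shortfall can shrink or reverse. The protocol does not say which INRs count.

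**The case against.** The strongest reply has four parts.

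- **Disclosure and the SAP.** The lack of in-hospital drug data is stated twice, and Section 4.1 defers detailed analysis to a separate SAP. A derived flag and a sensitivity table are ordinary SAP content. This limits the point but does not remove it: time zero and the start of exposure are fixed in the protocol itself, and the stated remedy covers only gaps and discontinuation.
- **Prevalence.** No share of in-hospital starts is given. AF diagnoses may date from 2005, and 4.1.2 Objective 2 has a category of more than 12 months from diagnosis to initiation, so many starts may be unrelated to the diagnosing admission. This stands, and it is why the size cannot be stated.
- **Direction and size.** A reader might infer that both results are understated, and that 3-33% of early events is the size of the error. The documents do not support that. They give no early hazard, the shifted window gains days at its end, and the sign for days to target depends on an unstated counting rule.
- **Reach.** Mortality is not an endpoint of Secondary Objective 1, and no effect on any hazard ratio has been shown. A reader might infer from the mixed time zeros that the Cox comparisons are biased; neither direction nor size follows from the documents.

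It would also be tempting to base the headline on patients with no recent admission. That would remove recently hospitalized patients, plausibly at higher risk, and could lower the early-risk estimate further.

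**Conclusion.** The point holds in a limited form. For new users started in hospital, the protocol's own rules place time zero after treatment began, and nothing in the text corrects for it. The 90-day window and the days to target are mislabelled for that group.

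First-90-day risk is likely understated if the hazard is highest just after starting; it is unbiased under a constant hazard. Days to target are likely too short if in-hospital INRs count toward the target. On the assumed inputs, the net shortfall in 90-day events is 0%, 7% or 25% in hospital starters. In the central case it is about 1-4% over all new users, with 20-60% started in hospital. Share, lag and early hazard are all assumptions. One secondary and one exploratory objective are affected; no primary result is shown to change.

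**What to change.** In 4.1.2 Objective 1 and 4.1.3 Objective 3:

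1. Keep all new users as the main analysis and describe its time zero as 'first outpatient purchase'.
2. Pre-specify a stratified sensitivity analysis. Flag new users with a hospital stay ending shortly before the first purchase (for example 14 days, with a second window as a check) or with a raised INR before it. The documents give no basis for any particular cut-off, so fix the windows and the INR threshold before analysis.
3. Report first-90-day rates and days to target separately for flagged and unflagged patients.
4. State whether INRs before purchase count toward the target. For flagged patients, repeat days to target with the start bounded by the admission date or the first in-hospital INR.

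The hospital dates and laboratory INRs are already requested (Sections 3.3 and 3.4.3), so the cost is wording in two subsections and one derived variable. If few patients are flagged, the main results stand largely as they are. The downside is smaller strata, and the flag will misclassify some outpatient starters who had an unrelated admission.
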